#### Sample Processing, Shipping, and Storage

The study sites will receive a sampling kit and laboratory manual with instructions on sample collection and processing. Details on storage conditions will be provided in the laboratory manual.

#### Assessments

In the future, additional genes, biomarkers, and analysis methods of interest will most likely be identified. It is therefore important not to restrict the utilization of this biologic material to current knowledge and retain the possibility of conducting other investigations as well. However, based on current knowledge, it is planned to utilize the material in the manner described in the following sections.

#### Whole Blood for DNA

Exome sequencing of deoxyribonucleic acid (DNA) will be performed on blood samples collected before initiation of UV1 vaccination. The DNA from normal cells will serve as a basis for comparison to DNA sequence from tumor tissue, allowing to detect tumor-specific DNA alterations.

#### **Use/Analysis of DNA**

- Genetic variation may impact a patient's response to therapy. Variable response to therapy may be due to genetic determinants that impact drug absorption, distribution, metabolism, and excretion; mechanism of action of the drug; disease etiology; and/or molecular subtype of the disease being treated. Therefore, where local regulations and Institutional Review Board/Independent Ethics Committee allow, a blood sample will be collected for DNA analysis.
- DNA samples will be used for research related to sargramostim and/or UV1 or metastatic malignant melanoma. Genetic research may consist of the analysis of one or more candidate genes or the analysis of genetic markers throughout the genome in relation to sargramostim and/or UV1.
- DNA samples will be analyzed as described in Section 8.4.1. Additional analyses may be conducted if it is hypothesized that this may help further understand the clinical data or help resolve issues with the clinical data.
- The samples may be analyzed as part of a multi-study assessment of genetic factors involved in the response to sargramostim and/or UV1 or study treatment of this class to understand study disease or related conditions.
- The results of genetic analyses will be reported in a separate study addendum.
- The Sponsor will store the DNA samples in a secure storage space with adequate measures to protect confidentiality.

• The samples will be retained while research on sargramostim and/or UV1 or study treatments of this class or indication continues but no longer than 5 years or other period as per local requirements.

#### Whole Blood for Analyses of Single Nucleotide Polymorphisms (SNPs)

Whole blood for analyses of SNPs will be taken prior to initiation of study treatment. Genomic DNA will be extracted and subsequently assessed for SNPs and other genetic variations in candidate genes that may predispose patients to benefit from the addition of UV1 vaccination to nivolumab and ipilimumab), or adverse events. Such genes include, but are not limited to hTERT, PD-1, PD-L1, PD-L2 and CTLA-4. Additional use of these data may include correlative analysis aimed at identifying genotypic associations with clinically relevant biomarkers identified by other methodologies.

#### Whole Blood for Peripheral Blood Mononuclear Cells (PBMCs)

Whole blood samples will be taken prior to initiation of study treatment and at designated timepoints for PBMC preparation. These samples may be used for immunophenotyping or characterization of the immune cell subsets in the periphery, including, but not limited to, T-cells, B cells, natural killer cells, myeloid-derived suppressor cells, or subpopulations of the aforementioned immune cell types. Additionally, these samples may be used for human leukocyte antigen typing, cytokine-release analyses, for functional immune cell tests, and characterization of the immune reactivity against tumor antigen.

#### **Tumor Tissue Specimens**

Tumor biopsies (formalin fixed, paraffin embedded [FFPE]) will form the basis for in situ characterization of the tumor and the tumor-microenvironment, including the tumor-infiltrating immune cells. The FFPE biopsies and snap-frozen biopsies will be used for DNA/RNA extraction and sequencing aiming at characterizing the immune contexture of the tumor, and to identify tumor-specific somatic mutations.

The biopsies should be collected from the *same lesion* at each timepoint of sampling (ie, it should be taken into consideration when selecting the lesion for tissue sampling that the lesion may shrink in response to therapy). Since heterogeneity within tumors is an issue, it should be aimed at sampling within the same area of the lesion at each sampling timepoint. If a previous biopsy site is noted in the specimen to be sampled, the biopsies should be taken from near that site, but not from the exact site, as biopsies may alter the biology of adjacent tissue. If the patient has only one target lesion, the biopsy should be taken either subsequent or at least 7 days prior to the screening imaging scan.

Biopsy samples should be excisional, incisional, or core needle. Punch biopsies are allowed as well. Fine needle aspirates or other cytology samples are only allowed after discussion with the Sponsor's biomarker expert. Biopsies may be done with local anesthesia or conscious sedation. Institutional guidelines for the safe performance of biopsies should be followed.

Detailed instructions of the obtaining, processing, labeling, handling, storage, and shipment of specimens will be provided in a separate Laboratory Manual.

#### **Fecal Samples**

Fecal samples will be collected prior to treatment to evaluate the gut microbiome by use of PCR amplification of candidate gene sequences. Planned exploratory analyses are subject to changes in line with scientific understanding and technical development.

#### **Delayed-type Hypersensitivity**

Patients in the experimental arm will be asked to measure area of skin irritation on the skin of the anterior forearm and record it on a patient diary card (details to be explained to patient). This will be done 48 ±4 hours after each DTH test injection according to timepoints described in Table 9. A positive DTH test is defined as an erythema and/or induration  $\geq$ 5 mm. The DTH patient diary card should be delivered to the study personnel at the next visit at the study site.

If a patient prematurely discontinues induction therapy, no more DTH testing will be performed for that patient.

## **Appendix 3 Eastern Cooperative Oncology Group Performance Status Scale**

East	ern Cooperative Oncology Group Performance Status
0	Fully active, able to carry on all pre-disease performance without restriction.
1	Restricted in physically strenuous activity but ambulatory and able to carry out work of a light or sedentary nature (eg, light housework or office work).
2	Ambulatory and capable of all self-care but unable to carry out any work activities. Up and about more than 50% of waking hours.
3	Capable of only limited self-care; confined to bed or chair more than 50% of waking hours.
4	Completely disabled. Cannot carry on any self-care. Totally confined to bed or chair.
5	Dead.

Appendix 4 Response Evaluation Criteria in Solid Tumors and Immune Response Evaluation Criteria in Solid Tumors

#### **RECIST 1.1 Response and Evaluation Endpoints**

Measurable Disease. Measurable tumor lesions (nodal, subcutaneous, lung parenchyma, solid organ metastases) are defined as those that can be accurately measured in at least one dimension (longest diameter to be recorded) as  $\geq 20$  mm with chest x-ray and as  $\geq 10$  mm with computed tomography (CT) scan or clinical examination. Bone lesions are considered measurable only if assessed by CT scan and have an identifiable soft tissue component that meets these requirements (soft tissue component  $\geq 10$  mm by CT scan). Malignant lymph nodes must be  $\geq 15$  mm in the short axis to be considered measurable; only the short axis will be measured and followed. All tumor measurements must be recorded in millimeters (or decimal fractions of centimeters). Previously irradiated lesions are not considered measurable unless progression has been documented in the lesion.

Non-measurable Disease. All other lesions (or sites of disease), including small lesions, are considered non-measurable disease. Bone lesions without a measurable soft tissue component, leptomeningeal disease, ascites, pleural/pericardial effusions, lymphangitis cutis/pulmonis, inflammatory breast disease, lymphangitic involvement of lung or skin, and abdominal masses followed by clinical examination are all non-measurable. Lesions in previously irradiated areas are non-measurable, unless progression has been demonstrated.

*Target Lesions.* When more than one measurable tumor lesion is present at Baseline, all lesions up to a maximum of 5 lesions total (and a maximum of 2 lesions per organ) representative of all involved organs should be identified as target lesions and will be recorded and measured at Baseline. Target lesions should be selected on the basis of their size (lesions with the longest diameter), be representative of all involved organs, but in addition should be those that lend themselves to reproducible repeated measurements. Note that pathological nodes must meet the criterion of a short axis of  $\geq 15$  mm by CT scan and only the short axis of these nodes will contribute to the baseline sum. All other pathological nodes (those with short axis  $\geq 10$  mm but <15 mm) should be considered non-target lesions. Nodes that have a short axis <10 mm are considered non-pathological and should not be recorded or followed. At Baseline, the sum of the target lesions (longest diameter of tumor lesions plus short axis of lymph nodes: overall maximum of 5) is to be recorded.

After Baseline, a value should be provided on the Case Report Form for all identified target lesions for each assessment, even if very small. If extremely small and faint lesions cannot be accurately measured but are deemed to be present, a default value of 5 mm may be used. If lesions are too small to measure and indeed are believed to be absent, a default value of 0 mm may be used.

Non-target Lesions. All non-measurable lesions (or sites of disease) plus any measurable lesions over and above those listed as target lesions are considered non-target lesions. Measurements are not required but these lesions should be noted at Baseline and should be followed as "present" or "absent."

*Response.* All patients will have their BEST RESPONSE from the start of study treatment until the end of treatment classified as outlined below:

Complete Response (CR): disappearance of target and non-target lesions and normalization of tumor markers. Pathological lymph nodes must have short axis measures <10 mm (Note: continue to record the measurement even if <10 mm and considered CR). Residual lesions (other than nodes <10 mm) thought to be non-malignant should be further investigated (by cytology specialized imaging or other techniques as appropriate for individual cases) before CR can be accepted. Confirmation of response is only required in non-randomized studies.

Partial Response (PR): at least a 30% decrease in the sum of measures (longest diameter for tumor lesions and short axis measure for nodes) of target lesions, taking as reference the baseline sum of diameters. Non-target lesions must be non-progressive disease (PD). Confirmation of response is only required in non-randomized studies.

Stable Disease (SD): Neither sufficient shrinkage to qualify for PR nor sufficient increase to qualify for PD taking as reference the smallest sum of diameters on study.

Progressive Disease (PD): at least a 20% increase in the sum of diameters of measured lesions taking as references the smallest sum of diameters recorded on study (including baseline) AND an absolute increase of  $\geq$ 5 mm. Appearance of new lesions will also constitute PD (including lesions in previously unassessed areas). In exceptional circumstances, unequivocal progression of non-target disease may be accepted as evidence of disease progression, where the overall tumor burden has increased sufficiently to merit discontinuation of treatment. Modest increases in the size of one or more non-target lesions are NOT considered unequivocal progression.

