#### Secondary Efficacy Analyses

Overall Survival will be analyzed in a fashion similar to that described for PFS at the time of the PFS analysis. Patients who withdraw consent to follow-up may have missing OS data. The impact of such patients on the analysis will be explored via imputation and possibly tipping point analyses. Full details will be provided in the SAP. Additionally, follow-up for survival will continue for a further 24 months after the PFS analysis at which time 60 deaths are expected to have accrued.

Objective Response Rate will be analyzed by exact logistic regression. Patients who have missing tumor assessment data leading to missing objective response data will be included in the analysis as non-responders.

Duration of Response will be analyzed via Cox regression modelling.

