# 6.2.3 New Anticancer Treatment

Details of any new anticancer treatments, from the time of the last dose of induction therapy until the earliest of either 70 PFS events reached or 18 months post last patient randomized, must be recorded in the eCRF. The reason for end of treatment for IMP and NIMP (nivolumab and ipilimumab) must be recorded.

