### 6.3 Treatment After Progressive Disease

Clinical evidence indicates that some patients treated with immune system-stimulating agents may develop PD by conventional response criteria (ie, pseudo-progression per iRECIST), before demonstrating clinical overall responses and/or SD. This may be explained by:

- Enhanced inflammation within tumors leading to increased tumor size which would appear as an enlarged index lesion and as newly visible small non-index lesions. Over time, both the malignant and inflammatory portions of the mass may then decrease leading to overt signs of clinical improvement.
- Initially, the kinetics of tumor growth may outpace anti-tumor immune activity. With sufficient time, the anti-tumor activity will dominate and become clinically apparent.

For patients who have initial radiological evidence of PD by RECIST 1.1 or iUPD (per iRECIST), it is at the discretion of the Investigator to keep the patient on induction/maintenance therapy (in the absence of clinical deterioration) until repeat imaging is obtained 4 to 8 weeks afterwards (iRECIST-based management). The decision to continue induction/maintenance therapy should only be made if the patient is assessed to be clinically stable, deriving clinical benefit, and tolerating the treatment.

At a minimum, patients must meet the following criteria for continuing induction/maintenance therapy after PD per RECIST 1.1/iUPD is identified:

- Absence of worsening symptoms and signs (including worsening of laboratory values)
- No decline in ECOG performance status
- Absence of rapid PD or of progressive tumor at critical anatomical sites (eg, cord compression) requiring urgent alternative medical intervention.

If repeat imaging fails to demonstrate iCPD (by iRECIST) and the patient continues to be clinically stable, induction/maintenance therapy should continue per protocol.

If repeat imaging demonstrates iCPD, induction/maintenance therapy should be discontinued.

The continuation/discontinuation of nivolumab as maintenance therapy will be recorded in the patients' medical file and in the eCRF.

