### 8.1.1.2 Tumor Assessments

Tumor assessments will be performed by the local Investigator/site and by BICR according to RECIST 1.1. In addition, the Investigator will evaluate new lesions and any potential PD by iRECIST (Appendix 4). For this protocol, target skin lesions are considered measurable only if measurable on CT or MRI. Measurable lesions that have previously been irradiated will not be considered target lesions unless size increase has been observed following completion of radiation treatment.

As a clarification to RECIST 1.1, the following applies if a lesion is resected or receives any form of treatment or local therapy during the study:

- The procedure itself, the pathology result (positive, negative, non-evaluable [NE]), and all post-procedure lesion assessments should always be recorded in the eCRF
- Subsequent assessments for such patients will be NE until PD has been determined from the nadir

Patients with PD per RECIST 1.1 and unconfirmed PD (iUPD) per iRECIST will have a new scan 4 to 8 weeks later to confirm PD per iRECIST (iCPD). A detailed description of response criteria is given in Appendix 4.

If confirmatory scan performed 4 to 8 weeks after iUPD does not confirm progression, further scans continue as originally planned.

Patient treatment will be determined by the Investigator. The BICR will perform assessments for statistical endpoint analysis only and will not interfere with Investigator assessments or treatment decisions. Treatment should continue until iCPD has been confirmed.

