#### **Objective Response Rate**

Objective response rate is defined as the proportion of patients with a best response of CR or PR (by BICR). The ORR will be analyzed by exact logistic regression. The model will include a single covariate for randomized treatment and covariates for baseline ECOG (0 versus 1) score. The exact odds ratio will be estimated from the model along with the associated 80% and 95% Cis and 2-sided p-value. Exact Clopper-Pearson 2-sided 80% and 95% confidence limits will be calculated for the proportion of patients with ORR in each arm.

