#### Duration of Response

Duration of response is defined as the time from first CR or PR (by BICR), whichever is recorded first, to progression (by BICR) or death from any cause, whichever occurs first. The DOR will be analyzed via Cox regression modelling with a fixed effect term for randomized treatment. The HR will be estimated from the model along with the associated 80% and 95% CI and 2-sided p-value. The data will also be displayed using Kaplan-Meier curves; median DOR and the 80% and 95% Cis will be estimated from the Kaplan-Meier curve by treatment arm. Since DOR is assessed in responding patients only, a supportive analysis will be performed

based on the expected duration of response as per Ellis et al  $(2008)^{32}$  as this analysis includes all randomized patients, including those who did not respond.

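### Appendix 4 limits best response to the on-treatment period, in conflict with the rest of the protocol; applied literally, it drops responses first seen after a stop without progression from ORR, and probably from DOR

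*Combined protocol and SAP*

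**What the plan says.** Appendix 4, under RECIST 1.1 Response and Evaluation Endpoints, sets a window before it lists the response categories: "All patients will have their BEST RESPONSE from the start of study treatment until the end of treatment classified as outlined below". Section 8.1.1.2 makes the appendix operative: "A detailed description of response criteria is given in Appendix 4".

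The end of treatment is not defined. Section 6.2.3 uses the term for several drugs at once, without fixing one date: "The reason for end of treatment for IMP and NIMP (nivolumab and ipilimumab) must be recorded".

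The endpoint definitions and the conduct sections contain no on-treatment limit:

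- **ORR (Section 9.4.2.2):** built on best response by BICR, with CR or PR counting as success. No start or end of the window is given.
- **Population (Section 9.3):** everyone randomized who has measurable disease, analyzed by randomized arm.
- **DOR (Section 9.4.2.2):** "Duration of response is defined as the time from first CR or PR (by BICR), whichever is recorded first". The same section says that DOR is evaluated only among responders. It adds a supportive expected-duration analysis, "as this analysis includes all randomized patients, including those who did not respond".
- **After a stop (Sections 7.2.1 and 7.3.2):** stopping induction is not leaving the study. Patients who stop for safety, or for any reason other than confirmed progression, go on to response follow-up visits.
- **Imaging (footnote i of Tables 5 and 6; Section 8.1.1.1):** scans go ahead whether or not treatment has stopped, and scheduled images go to BICR.

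Section 9.4.1 leaves further detail to a separate SAP, whose text is not in the documents.

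**The concern.** ORR rests on best response, and the only place that says over what period best response is taken confines it to treatment. Yet the protocol keeps scanning patients who have stopped and sends the scheduled images for central reading. An analyst who follows Appendix 4 to the letter would discard BICR responses that the trial went to the trouble of collecting.

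On that reading, ORR would depend partly on when open-label treatment stopped and not only on whether the tumor responded. Stops without progression are foreseen by design: Section 7.2.1 has its own pathway for permanent discontinuation for safety. This goes beyond missing detail, because a stated rule, if followed, gives an ORR that does not match the all-randomized population of Section 9.3.

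**Working it through.** **1. Figures in the plan.** The protocol gives no assumed ORR, no ORR power, and no rate of stopping or of late response, so there is no ORR figure to reproduce. Its one design figure is 70 PFS events (HR 0.60, one-sided alpha 0.10, 80% power, 1:1). Schoenfeld: 4 × (1.2816 + 0.8416)² / (ln 0.60)² = 18.03 / 0.261 = 69.1, rounded up to 70. It reproduces, and this point does not touch it.

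**2. Who is affected.** All four conditions must hold:

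- the patient is off treatment;
- there has been no RECIST 1.1 progression (the RECIST 1.1 and iRECIST comparison in Appendix 4 already bars a response after progression);
- no CR or PR was recorded before the stop;
- a CR or PR is seen at a later scan.

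**3. Whether the schedule lets this happen.** The first scheduled post-baseline scan is at Week 12, which is 84 days after randomization. With randomization on Day 1 that is Day 85 (Days 78 to 92 with the ±7-day window). With randomization 3 days earlier it is Day 82 (Days 75 to 89).

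Days from the last nivolumab-ipilimumab dose to a Week 12 scan on Day 85:

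| Last cycle given | Control dose day | Gap | Experimental dose day | Gap |
|---|---|---|---|---|
| 1 | 1 | 84 | 10 | 75 |
| 2 | 22 | 63 | 31 | 54 |
| 3 | 43 | 42 | 52 | 33 |
| 4 | 64 | 21 | 73 | 12 |

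Maintenance is due 6 weeks (42 days) after the last induction dose: Day 64 + 42 = Day 106 in control and Day 73 + 42 = Day 115 in the experimental arm. So a patient who stops permanently for safety during induction would generally have every scheduled post-baseline scan after the last dose. The cycle 4 row matters only for patients who never start maintenance. Table 5 lists an additional scan at premature discontinuation; it may capture some responses, depending on how the end of treatment is dated.

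**4. Unit of effect on ORR.** 154 / 2 = 77 patients per arm, all required by Section 5.1 to have a measurable lesion. One uncounted response is 1/77 = 1.3 percentage points of that arm's ORR.

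For scale only, with counts that are assumptions and not in the documents: 3, 5 or 8 uncounted responses in an arm give 3/77 = 3.9, 5/77 = 6.5 or 8/77 = 10.4 points. If 5 were uncounted in one arm and 2 in the other, the ORR difference would move by 3/77 = 3.9 points. The same number in each arm would leave the difference unchanged.

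**5. What happens to DOR.** The DOR start date has no on-treatment limit, but DOR is confined to responders. If responders are the patients counted in ORR, a late responder drops out of both endpoints.

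**The case against.** The best defense is that Appendix 4 supplies response criteria and does not define the ORR analysis. Much of it is generic RECIST text: it mentions chest x-ray measurability, inflammatory breast disease and tumor markers. Section 9 defines ORR without an on-treatment limit, and the conduct sections consistently expect response to be followed after a stop. On this view the phrase is a leftover, and a SAP that we cannot see may settle it.

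Most of that stands. An editorial inconsistency is more likely than a deliberate choice of on-treatment ORR, and nothing shows that the sponsor chose one. But where Appendix 4 is generic on measurability, Sections 5.1 and 8.1.1.2 override it expressly. No section does so for the best-response window, and a SAP that set a different one would contradict the protocol.

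Three stronger readings are tempting, and the documents do not support them:

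- **That ORR and DOR would use different responders.** A reader might infer this because DOR starts at the first BICR response whenever it occurs. Section 9.4.2.2 limits DOR to responders, so late responders would more naturally leave both endpoints.
- **That the missing-data rule would turn these patients into non-responders.** The Synopsis says: "Patients who have missing tumor assessment data leading to missing objective response data will be included in the analysis as non-responders". A patient scanned at Week 12 and read by BICR has tumor assessment data. Calling that scan missing presupposes the disputed window.
- **That the Week 12 scan falls outside the window for nearly everyone.** This would follow if treatment ended with induction. Section 6.3 treats induction and maintenance as one continuing course: "If repeat imaging demonstrates iCPD, induction/maintenance therapy should be discontinued". A patient who has finished cycle 4 and is waiting for maintenance is then still on treatment at Week 12.

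**Conclusion.** The point holds as a minor one. Appendix 4 states the only best-response window, leaves its end undefined, and conflicts with Sections 7.2.1, 7.3.2, 9.3 and 9.4.2.2 and with the imaging footnotes. Applied literally, it would leave out of ORR, and probably of DOR, any CR or PR first seen after a stop without RECIST 1.1 progression. The clearest case is a safety stop during induction, before the Week 12 scan at about Day 85.

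Size and direction cannot be determined from the documents. The unit is about 1.3 percentage points of an arm's ORR per uncounted response, assuming 77 patients per arm. The group is narrow, and only secondary response endpoints, which carry no stated power, are affected; PFS, OS and the event count are not. The conclusion assumes that treatment includes maintenance and that no SAP text replaces the window.

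**What to change.** In Appendix 4, and in matching words in Section 9.4.2.2 and the SAP, replace the on-treatment window with: best BICR RECIST 1.1 response from randomization until BICR progression or the PFS cut-off date, whichever is first, regardless of discontinuation of study treatment. State that ORR and DOR use this one responder set, which the supportive expected-duration analysis also needs.

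Optionally, add a sensitivity analysis that counts only responses first seen before new anticancer treatment, parallel to the first PFS sensitivity analysis in Section 9.4.2.1.

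The cost is a short wording change in Appendix 4, repeated in Section 9.4.2.2 and the SAP. The images are already collected and sent to BICR, so no new data are needed, and nothing in treatment or follow-up changes.
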